#### **7.1.2.1 Crossover**

Patients in the control arm will be allowed to crossover to PDR001 treatment if they have radiological progression (as per RECIST v1.1) documented by an independent central review and the investigator believes this is the best treatment option for the patient. The End of Treatment (EoT1) visit assessments should be performed as described in [Section 7.1.3](#) before a patient can receive PDR001 treatment.

Patients should receive PDR001 within 21 days of the last radiological assessment, if they have no Grade 3/4 AEs and brain metastases. Each case must be first discussed with Novartis. No other antineoplastic therapies are allowed from the time of disease progression to the time of

crossover treatment initiation and throughout PDR001 treatment. Once transitioned to PDR001 treatment, patients will attend the clinic for treatment and safety monitoring as described in [Section 7.2.2](#).

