## **Data analysis after crossover**

For patients who crossover to PDR001 after progression as per RECIST v1.1 to chemotherapy in the control arm, the data will be presented in listings separately from the randomized part of the study. If there are at least 10 patients crossing over, summary tables may be presented with frequency count and percentage for categorical data and descriptive statistics for continuous data. For these patients, the date of their first dose of PDR001 will be used as the starting date to define their safety and efficacy endpoints (such as ORR, irPFS and OS). Details will be provided in the RAP.

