2.1 Data analysis general information

The data will be analyzed by Novartis personnel and/or designated CRO(s) using the most updated version of SAS, R and JAGS. PK parameters will be calculated using non-compartmental methods available in most updated version of Phoenix WinNonlin.

Data from participating centers in this study protocol will be combined, so that an adequate number of patients will be available for analysis. No center effect will be assessed. The data will be summarized with respect to demographic and baseline characteristics, efficacy observations and measurements, safety observations and measurements, and all relevant pharmacokinetic (PK) and pharmacodynamics (PD) measurements using descriptive statistics (n, mean, standard deviation, median, minimum, and maximum) for quantitative data and contingency tables (frequencies and percentages) for qualitative data.

Data will be summarized and listed by study arms or by study treatment groups. Details are specified in each of the subsections.

Study arms refer to

- PDR001
- Chemotherapy

Study treatment groups refer to

- PDR001
- Chemotherapy
- Crossover

Crossover treatment group consists of the patients in the chemotherapy arm who crossover to PDR001 and treated with PDR001 after progression to chemotherapy. The clinical data collected before the crossover will be summarized in the chemotherapy treatment group; the clinical data collected after the crossover will be summarized or listed as appropriate in crossover treatment group.

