2.1.1 General definitions

Study drug and study treatment

Study drug refers to PDR001. Study treatment refers to both PDR001 and Chemotherapy. Chemotherapy used in control arm may differ across centers.

Date of first/last administration of study drug and study treatment

The date of first (last) administration of study treatment is derived as the first (last) date when a non-zero dose of study treatment was administered and recorded on the Dosage Administration Record (DAR) eCRF. For the sake of simplicity, the date of first (last) administration of study treatment will also be referred as start (last) date of study treatment.

Study day

For PDR001 and Chemotherapy treatment group:

The study day for safety assessments/events will be calculated using the start date of study treatment as reference. The study day for efficacy assessments/events will be calculated using the date of randomization as reference.

For safety assessments/events occurring on or after the start date of study treatment, study day will be calculated as:

$$\text{Study day (days)} = \text{Event date} - \text{Start date of study treatment} + 1$$

Therefore, the first day of study treatment is study day 1.

For safety assessment/events occurring prior to the start of the study treatment, study day will be negative and will be calculated as:

$$\text{Study day (days)} = \text{Event date} - \text{Start date of study treatment}$$

For efficacy assessments/events occurring on or after randomization, study day will be calculated as:

$$\text{Study day (days)} = \text{Event date} - \text{Date of randomization} + 1$$

For efficacy assessment/events occurring prior to randomization, study day will be negative and will be calculated as:

$$\text{Study day (days)} = \text{Event date} - \text{Date of randomization}$$

Study day will be displayed in the data listings.

For Crossover treatment group:

The study day for safety and efficacy assessments/events will be calculated using the start date of PDR001 treatment as reference.

For assessments/events occurring on or after the start date of PDR001 treatment, study day will be calculated as:

Study day (days) = Event date – Start date of PDR001 treatment + 1

Therefore, the first day of PDR001 treatment is study day 1.

For assessment/events occurring prior to the start of the PDR001 treatment, study day will be negative and will be calculated as:

Study day (days) = Event date – Start date of PDR001 treatment

On-treatment assessment/event

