2.7 Analysis of the secondary efficacy variables

Evaluation of anti-tumor activity will be based on central review of overall lesion response according to RECIST v1.1 (see [CPDR01X2201-Protocol-Appendix 1](#)) and irRC ([CPDR01X2201-Protocol-Appendix 2](#)). The variables used to evaluate anti-tumor activity are OS, ORR, BOR, DOR, TTP as per RECIST v1.1 and irPFS as per irRC. Summaries and listings described in this section will be done by study arms based on the FAS.

Individual lesion measurements, overall lesion response, OS, DOR, and irPFS will be listed by patient. OS, ORR, BOR, DOR, TTP and irPFS will be summarized as per specification in [Table 2-3](#). A waterfall plot of best percentage change from baseline in sum of longest diameters of target lesions per RECIST 1.1 and total measured tumor burden (TMTB) per irRC ([CPDR01X2201-Protocol-Appendix 2](#)) will be presented for each study treatment group.

Table 2-3 Analysis of the secondary efficacy variables

Endpoint	Definition	Analysis
----------	------------	----------

OS	Time from the date of randomization to date of death due to any cause. If a patient is not known to have died, survival will be censored at the date of last known date patient alive.	A Kaplan-Meier plot for OS will be presented. Median OS (in months) with corresponding 95% CI, 25th and 75th percentiles (Brookmeyer and Crowley 1982, Klein and Moeschberger 1997) and Kaplan-Meier estimated probabilities (OS rate) with corresponding 95% CIs (Greenwood's formula, Kalbfleisch and Prentice 1980) at several time points (6, 12, 18 and 24 months) will be presented. The number (%) of deaths and patients censored will also be summarized.
irPFS (per irRC)	Time from the date of randomization to the date of the first documented disease progression (irPD) (CPDR01X2201-Protocol-Appendix 2), or death due to any cause.	Median irPFS (in months) with corresponding 95% CI, 25th and 75th percentiles (Brookmeyer and Crowley 1982, Klein and Moeschberger 1997) and Kaplan-Meier estimated probabilities (irPFS rate) with corresponding 95% CIs (Greenwood's formula, Kalbfleisch and Prentice 1980) at several time points (2, 4, 6, 8 and 12 months) will be presented. The number (%) of progressions, deaths and patients censored will also be summarized. The analysis of irPFS will be done for PDR001 arm and crossover patients if there are more than 10 crossover patients.

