5.1 Baseline

For PDR001 and Chemotherapy arm:

For safety assessments/events, baseline is the last available and valid assessment performed or value measured within 28 days before the first administration of study treatment, unless otherwise stated under the related assessment section. For demographic data (including age, sex, race, ethnicity, height, baseline weight and ECOG performance status) baseline value outside the 28 days window may be reported as long as it is the last available and valid assessment performed or value measured before the first administration of study treatment. Baseline can be the day before first treatment administration or the same day as first treatment administration if a pre-dose assessment/value is available (e.g., ECG, PK samples, samples for biomarkers).

If time is recorded for the first treatment dose and for a specific assessment performed the day of first dose, this assessment will be considered as baseline only if it is actually performed before the first dose, as checked using both times.

If time is not recorded, a specific assessment performed the day of first dose administration will be considered as baseline if, according to protocol, it should be performed before the first dose.

Patients with no data on a particular parameter before the first treatment administration will have a missing baseline for this parameter.

For efficacy assessments/events, baseline is the last available and valid assessment performed or value measured within 28 days before the date of randomization. If pre-randomization assessment is not available, assessment within 7 days after randomization can also be considered as baseline assessment.

For crossover treatment group:

For safety and efficacy assessments/events: baseline is the last available and valid assessment performed before PDR001 dosing.

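### The irPFS row of SAP Table 2-3 covers crossover patients but starts their clock at randomization, against the protocol's rule that it starts at the first PDR001 dose

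*SAP*

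**What the plan says.** The irPFS row of Table 2-3 (SAP 2.7) has a Definition column and an Analysis column. The definition is "Time from the date of randomization to the date of the first documented disease progression (irPD"), or death from any cause. The Analysis column lists the median, quartiles and the 2, 4, 6, 8 and 12-month rates, and ends: "The analysis of irPFS will be done for PDR001 arm and crossover patients if there are more than 10 crossover patients". No separate start date is given for crossover patients.

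Four other places bear on that start date:

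- **Protocol section 10, Data analysis after crossover.** For patients who move from chemotherapy to PDR001, "the date of their first dose of PDR001 will be used as the starting date to define their safety and efficacy endpoints". The endpoints are illustrated by "such as ORR, irPFS and OS". Details are left to the analysis plan.
- **SAP 2.1.1, crossover group.** "The study day for safety and efficacy assessments/events will be calculated using the start date of PDR001 treatment as reference".
- **SAP 5.1, crossover group.** For safety and efficacy, "baseline is the last available and valid assessment performed before PDR001 dosing".
- **SAP 2.1.** Data from before the switch go to the chemotherapy group, and "the clinical data collected after the crossover will be summarized or listed as appropriate in crossover treatment group".

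SAP section 4, which is meant to record changes from the protocol's analyses, covers COVID-19 only.

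**The concern.** A crossover irPFS estimate is meant to show how long PDR001 holds the disease in patients whose tumor has already progressed on chemotherapy. It does so only if the clock starts when PDR001 starts. The row that a programmer would use to derive the endpoint starts it at randomization, when every one of these patients was about to receive chemotherapy. It does so while naming crossover patients as a group to be analyzed.

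The protocol had settled the question the other way and left the details to the analysis plan. The plan is therefore where the rule should appear, and the row states a different one without declaring a change. At stake are the crossover median and the five landmark rates, which would be reported for the same endpoint as the PDR001 arm and could be read alongside it.

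**Working it through.** The plan states no crossover irPFS figure, so there is nothing to reproduce. The check is a comparison of text, followed by an illustration of size.

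**Step 1. Which start date does each place set for crossover patients?**

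| Place | Sets | Reference point |
|---|---|---|
| Protocol section 10, after crossover | endpoint start date, irPFS named | first PDR001 dose |
| SAP 2.1.1 | study day | PDR001 start |
| SAP 5.1 | baseline | last assessment before PDR001 |
| SAP 2.1 | which data enter the group | after crossover |
| SAP Table 2-3, irPFS row | endpoint start date | randomization |

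Only the first and last rows define the endpoint's origin, and they disagree. Study day and baseline are separate quantities. Resetting them points to PDR001 as the intended origin but does not define irPFS.

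**Step 2. What does the row give if followed literally?** It depends on where irPD is looked for.

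- *Reading A: irPD is sought only after crossover, against the reset baseline.* SAP 5.1 and 2.1 suggest this. Each patient's time is then C + L + X. C is the time from randomization to the last scan on chemotherapy, L is the lag from that scan to the first PDR001 dose, and X is irPFS from that dose. The excess is C + L.
- *Reading B: the first irPD after randomization counts, wherever it falls.* Protocol 7.2.1 has tumors assessed under both RECIST v1.1 and irRC. irPD needs confirmation at least 4 weeks later, and Protocol 10.5.2 dates a confirmed irPD to the first of the two scans. A progression on chemotherapy that was confirmed later would then end irPFS before PDR001 began. Against this, Protocol Table 7-2 schedules only RECIST v1.1 evaluation for the chemotherapy arm.

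Reading A lengthens crossover irPFS and Reading B cuts it off. Neither estimates X.

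**Step 3. Size under Reading A.** The documents do not report C for patients who crossed over. Inputs:

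- C: exponential, with an assumed median of 2 to 5.5 months. The upper end is the planning median for the whole control arm (Protocol 10.4.2). The lower end is close to the first scan at week 8.
- L: uniform on 0 to 21 days, from Protocol 7.1.2.1 ("Patients should receive PDR001 within 21 days of the last radiological assessment"). 21 / 30.44 = 0.69 months.
- X: exponential, with an assumed median of 2 or 4 months.
- C, L and X independent; 2,000,000 simulated patients per row.

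| Median C (months) | True median X (months) | Median of C + L + X | 6-month rate, true | 6-month rate, from randomization |
|---|---|---|---|---|
| 2 | 2 | 5.2 | 12.5% | 42% |
| 5.5 | 2 | 9.0 | 12.5% | 69% |
| 2 | 4 | 7.4 | 35% | 61% |
| 5.5 | 4 | 11.8 | 35% | 80% |

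The true 6-month rate follows directly: 2^(−6/4) = 0.354 for a 4-month median. For that median the true 2-month rate is 2^(−2/4) = 0.707; from randomization it would be about 94% to 97%.

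**Step 4. What is not affected.** Primary PFS, the event count, power and alpha do not use the crossover clock.

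**The case against.** The strongest reply is that this is a drafting gap, not a chosen analysis. Protocol section 10 names irPFS and fixes the start date. The SAP's study-day, baseline and data-split rules for the crossover group all fit that date. SAP 2.7 says its summaries are by study arm on the FAS, and crossover is a treatment group, not an arm. The Definition column can therefore be read as written for the arms, with crossover added later under Analysis. The derivation itself sits in the programming dataset specifications, which are not public and may already use the right date. Silence in section 4 is also what one would see if no change was intended.

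Much of this stands, and it rules out stronger claims that a reader might infer:

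- *That chemotherapy time is in fact counted as irPFS on PDR001.* The documents show what the row says, not what was programmed, and the surrounding text points to PDR001 start.
- *That the chemotherapy interval is event-free by construction.* Survival to crossover is guaranteed, but freedom from irPD is not. Under Reading B, progression on chemotherapy is itself the event.
- *That the typical excess is 5.5 to 6 months.* That applies a planning median for the whole control arm to a selected subset: patients who progressed by central review, survived, and were judged suitable for PDR001. The 21-day limit also runs from the last scan, which need not be the scan that showed progression.

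What does not stand is the suggestion that nothing needs changing. The row names crossover patients and gives them one origin, which contradicts the protocol. No sentence in the SAP states the correct one.

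**Conclusion.** The inconsistency is established from the text: the irPFS row applies a randomization origin to crossover patients, the protocol requires the first PDR001 dose, and the SAP neither restates that rule nor declares a departure from it. Used as written, the row cannot yield irPFS on PDR001 for these patients.

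The direction of the error depends on how irPD is searched for. Under Reading A, a true median of 4 months would be reported as about 7 to 12 months. That range rests on assumed exponential, independent times and an assumed chemotherapy median of 2 to 5.5 months; the actual excess is each patient's interval from randomization to first PDR001 dose, which the documents do not give. Under Reading B, irPFS would end before PDR001 starts.

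The consequence is limited. irPFS is secondary, and the crossover summary is descriptive and produced only with more than 10 crossover patients. The documents do not report how many crossed over in total. The SAP plans no test or hazard ratio between crossover patients and the PDR001 arm. This should be corrected before any crossover irPFS is reported, but it does not touch the trial's main conclusion.

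**What to change.** Add one sentence to the irPFS row of SAP Table 2-3:

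> For crossover patients, irPFS is the time from the first dose of PDR001 to first irPD or death after that dose, using the pre-PDR001 baseline (section 5.1).

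Keep randomization as the origin for the PDR001 arm. Use the first PDR001 dose as the start date for any other crossover efficacy output, and check that the dataset specification derives it that way.

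While the row is open, align the threshold for producing crossover summaries: the protocol says at least 10 patients, the SAP more than 10.

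The cost is one sentence and one derivation check. No sample size, event count or error rate changes. If the derivation already uses the first PDR001 dose, no result changes either.

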2.8 Safety analysis

Summaries and listings described in this section will be done by study treatment groups based on the Safety set:

- PDR001
- Chemotherapy
- Crossover

For crossover treatment group, summaries will be done if there are more than 10 crossover patients.

The assessment of safety is based on the type and frequency of Adverse Events (AEs) as well as on the number of laboratory values that fall outside of pre-determined ranges (Common Toxicity Criteria for Adverse Events (CTCAE) grading limits or normal ranges as appropriate). Other safety data include electrocardiogram and vital signs.

The overall observation period will be divided into three mutually exclusive segments:

- Pre-treatment period: from day of patient's informed consent to the day before first dose of study treatment,
- On-treatment period: from day of first dose of study treatment to the end of safety follow up, i.e., for PDR001, to 30 days after last dose of PDR001; For chemotherapy, to 30 days after last dose of chemotherapy.

- Post-treatment period: starting at Day 31 after last dose of PDR001 for PDR001 treatment group; Starting at Day 31 after last dose of chemotherapy for chemotherapy treatment group.

If dates are incomplete in a way that clear assignment to pre-, on-, post-treatment period cannot be made, then the respective data will be assigned to the on-treatment period.

Safety summaries will primarily be based on all data from the on-treatment period. Following last administration of PDR001, adverse events (including serious adverse events), and new antineoplastic therapies are collected for a period of 150 days. Following start of new antineoplastic therapy only treatment related adverse events will be collected. Select summaries of related adverse events will be produced for the combined on-treatment and post-treatment periods ([Section 2.8.1](#)).

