#### **7.1.5 Follow up for safety evaluations**

All patients in the PDR001 treatment arm must have safety evaluations for 150 days after the last dose of study treatment. Patient in the Chemotherapy arm must have safety evaluations for 30 days after the last dose of study treatment.

Patients in the control arm who crossover are not required to have a 30-day safety follow-up performed and can crossover as soon as the End of Treatment (EoT1) visit is complete. Once patients discontinue PDR001 crossover treatment, safety follow-up must be performed for 150 days after the last dose of PDR001.

The evaluations can be done either by telephone call or visit for the 30-, 90-, and 150-day safety follow-up visits for the PDR001 arm and crossover patients. Concomitant medications will be collected until the 30- day safety follow-up has been completed or the start of a new antineoplastic therapy, whichever occurs first. A PK and immunogenicity sample should be collected at 150 days for PDR001 arm patients only, as described in [Section 7.2.3](#). If the 150-day safety evaluation is conducted by phone, samples do not need to be collected.

Data collected during the Safety follow up period should be added to the Adverse Events eCRF, Concomitant Medications eCRF, Antineoplastic therapies since discontinuation of study drug eCRF (including tumor directed surgical procedures) and Unscheduled blood collection for PK and IG eCRFs. All AEs suspected to be related to study treatment should be followed weekly, or as clinically indicated, until resolution or stabilization. For female patients of child bearing potential, pregnancy tests will be performed as outlined in [Section 7.2.2.5](#).

The safety follow-up will not be performed for patients who transfer to another study or to an alternative treatment option to continue provision of study treatment.

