For PDR001 arm, an on-treatment assessment/event is defined as any assessment/event obtained in the time interval from the start date of study treatment until the minimum date of (last date of study treatment + 30 days).

For crossover treatment group, an on-treatment assessment/event is defined as any assessment/event obtained in the time interval from the start date of PDR001 treatment until the minimum date of (last date of study treatment + 30 days).

For chemotherapy arm, an on-treatment assessment/event is defined as any assessment/event obtained in the time interval from the start date of study treatment until the minimum date of (the last date of study treatment + 30 days inclusive, start of crossover PDR treatment if crossed over).

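### SAP 2.8 omits the crossover cut that SAP 2.1.1 applies to the chemotherapy on-treatment period, so early crossover PDR001 events could be tabulated under chemotherapy if 2.8 is programmed as written

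*SAP*

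**What the plan says.** The SAP defines the chemotherapy on-treatment period twice.

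- SAP 2.1.1 (General definitions) takes the minimum of two dates: "the last date of study treatment + 30 days inclusive, start of crossover PDR treatment if crossed over". The same section defines a crossover on-treatment period, from the first PDR001 dose to 30 days after the last dose.
- SAP 2.8 (Safety analysis) gives one date only: "For chemotherapy, to 30 days after last dose of chemotherapy". Its post-treatment period follows on from this: "Starting at Day 31 after last dose of chemotherapy for chemotherapy treatment group". Neither mentions crossover.

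Section 2.8 governs the safety tables: "Safety summaries will primarily be based on all data from the on-treatment period".

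SAP 2.1 divides the data at crossover. For the earlier part, "The clinical data collected before the crossover will be summarized in the chemotherapy treatment group"; for the later part, "the clinical data collected after the crossover will be summarized or listed as appropriate in crossover treatment group".

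Protocol 7.1.5 excuses crossover patients from the 30-day safety follow-up and says that they "can crossover as soon as the End of Treatment (EoT1) visit is complete".

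**The concern.** Two definitions of one period, in one document, give different answers for the same patient. They differ only for patients who start PDR001 within 30 days of their last chemotherapy dose, and the protocol allows that. For such a patient, an adverse event in the first days of PDR001, an infusion reaction for example, lies inside the 2.8 chemotherapy on-treatment period and also belongs to the crossover group under 2.1.

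If 2.8 drives the derivation, the event could appear in both columns, or only under chemotherapy. Either outcome would add events arising on PDR001 to the chemotherapy rates, which flatters PDR001 in the descriptive comparison that serves a secondary objective.

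**Working it through.** The plan states no figure on this point, so there is none to reproduce. The check compares the definitions and then does the date arithmetic.

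**Can the overlap occur?**
- Protocol 7.1.5: crossover may follow EoT1 directly, with no 30-day wait.
- Protocol 7.1.3: EoT1 falls within 14 days of the last dose, or of the decision to stop.
- Protocol 7.1.2.1: PDR001 should start within 21 days of the last scan. That clock runs from the scan and not from the last dose.

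Overlap is therefore possible. The interval from last chemotherapy dose to first PDR001 dose is not given, so it is an assumption here.

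**How long is it?** Let d be the number of days from last chemotherapy dose to first crossover PDR001 dose. The 2.8 window runs through day 30 and PDR001 starts on day d. Counting both end days:

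overlap under 2.8 = max(0, 30 − d + 1)

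For example, 30 − 7 + 1 = 24, 30 − 14 + 1 = 17 and 30 − 21 + 1 = 10.

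| Assumed d (days) | PDR001 days in chemotherapy window, SAP 2.8 | SAP 2.1.1, start day excluded | SAP 2.1.1, start day included |
|---|---|---|---|
| 1 | 30 | 0 | 1 |
| 7 | 24 | 0 | 1 |
| 14 | 17 | 0 | 1 |
| 21 | 10 | 0 | 1 |
| 28 | 3 | 0 | 1 |
| 30 | 1 | 0 | 1 |
| 31 or more | 0 | 0 | 0 |

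For every d up to 30 the first infusion is inside the 2.8 window. The last column shows a smaller gap in 2.1.1 itself: it ends the window at "start of crossover PDR treatment if crossed over" without saying which period owns that day, which is the day of the first infusion.

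**Which outputs are exposed?**
- *Adverse event tables.* The crossover scenarios in SAP 2.8.1 say when an event counts in the PDR001 period. They do not say that it leaves the chemotherapy period.
- *Crossover column.* SAP 2.8 produces crossover summaries only with more than 10 crossover patients. With 10 or fewer, an event caught by the 2.8 window would be tabulated under chemotherapy alone.
- *Deaths.* SAP 2.8.1 summarizes on-treatment deaths by treatment arm. SAP 2.1 recognizes two arms, with crossover existing only as a treatment group. A death soon after crossover would sit in the chemotherapy arm's on-treatment table.
- *Registry tables.* The EudraCT and clinicaltrials.gov tables in SAP 2.8.1 also use the on-treatment period.

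**What does one patient weigh?** The protocol's study status gives 122 randomized, 82 of them to PDR001, so the control arm has 122 − 82 = 40. With a denominator of at most 40, one misplaced patient moves a chemotherapy percentage by at least 1/40 = 2.5 points. Crossover did occur: the Amendment 05 study status reports 4 crossover patients ongoing at 10 August 2018. The total, and the number crossing within 30 days, are not given.

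**The case against.** The best reply is that the SAP, read as a whole, already settles the matter. Section 2.1 splits the data at crossover, and 2.8 says its summaries follow those treatment groups. Section 2.1.1 truncates chemotherapy at crossover and defines the crossover window. The scenarios in 2.8.1 treat chemotherapy as Period 1 and PDR001 as Period 2, and count new or worsening events in Period 2. Protocol Section 10, on data after crossover, starts the safety clock at the first PDR001 dose. The diagram that goes with the scenarios is not in the available text, and the derivations sit in a separate programming specification; either may state where Period 1 ends.

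Much of this stands. A reader of 2.8 alone might infer that early PDR001 events will be counted as chemotherapy events, that this happens routinely, and that the safety comparison is therefore biased. The documents support none of these as fact. The other sections point to the crossover group, and early crossover is permitted without any statement of how often it occurs. The open-ended chemotherapy post-treatment period also matters little: the combined on- and post-treatment event summaries are produced for PDR001, which leaves mainly listing flags and the all-deaths table.

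The conflict itself remains. No text removes an event from chemotherapy once it is counted in the crossover period, and the crossover column is conditional. The death tables are worded by arm; that may be loose wording for group, but the SAP does not say so. Protocol 10.5.3.1 also lacks the cut, so a programmer who checked 2.8 against the protocol would find it confirmed.

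**Conclusion.** SAP 2.8 contradicts SAP 2.1.1 on when the chemotherapy on-treatment period ends for patients who cross over, and it sits badly with the split in SAP 2.1. Programmed as written, 2.8 would place up to 30 days of PDR001 exposure, including the first infusion, in the chemotherapy window: 24, 17 or 10 days for assumed gaps of 7, 14 or 21 days. Events in that stretch could be counted twice or charged to chemotherapy, with on-treatment deaths the most exposed.

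This rests on 2.8 being taken literally and on some patients starting PDR001 within 30 days of their last chemotherapy dose. The size of any effect on the tables cannot be computed, because the number of such patients is not reported. Misattribution is a possibility that the wording leaves open, not an outcome that the plan prescribes. The correction should be made because the SAP already contains the right rule in another section.

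**What to change.** 1. In SAP 2.8, for patients who cross over, end the chemotherapy on-treatment period at the earlier of last chemotherapy dose + 30 days and the day before the first crossover PDR001 dose. End any chemotherapy post-treatment period no later than the day before that dose.
2. Leave both periods unchanged for patients who do not cross over. Their post-treatment period must still begin at Day 31.
3. Refer from 2.8 to 2.1.1 for the crossover on-treatment period, which is already defined there.
4. Amend 2.1.1 so that the day of the first PDR001 dose belongs to the crossover period.
5. In the on-treatment death table, report deaths after the first crossover dose under the crossover treatment group, or flag them separately.

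The cost is a few lines of SAP text, a one-line change in the period derivation, and a small change to the death table shell. No new data are needed.
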